#### Note

ONO-4538 is co-developed by Ono Pharmaceutical Co., Ltd. and Bristol-Myers Squibb (BMS) (BMS code: BMS-936558). ONO-4538 is described in this document as a compound code.

Ethics

This study will be conducted in compliance with the ethical principles that have their origin in the Declaration of Helsinki, the study protocol, standards stipulated under ICH Good Clinical Practice Guidelines (GCPs), the applicable local regulatory requirements and revised ordinances and relevant notifications.

This protocol will be amended when revision is needed to ensure the safety conduct of the study.

## Protocol Synopsis

**1. Study Objectives**

The objective of the study is to investigate the pharmacokinetics of ONO-4538 administered to Korean patients with advanced or recurrent solid tumors who are refractory or intolerant to standard therapy or for whom no appropriate treatment is available.

**2. Study Design**

Multicenter, open label, uncontrolled study

**3. Disease Studied****3.1 Disease**

Advanced or recurrent solid tumors

**3.1.1 Subject Inclusion Criteria**

Patients satisfying all the following criteria will be included:

1. Male or female (Korean)
2.  $\geq 20$  years of age (at time of obtaining the Informed Consent)
3. Histologically or cytologically confirmed solid tumor
4. Patients with advanced or recurrent solid tumors who are refractory or intolerant to standard therapy or for whom no appropriate treatment is available
5. ECOG Performance Status (Appendix 2) is 0 to 1
6. Life expectancy is  $\geq 90$  days at time of patient enrollment
7. Women of childbearing potential (including women who are amenorrheic due to chemical menopause or for another medical reason)\*1 must agree to engage in contraception\*2 from the time of informed consent to at least 400 days after the final dose of the investigational product.
8. Men must agree to use a contraceptive from the start of study treatment until at least 400 days following the last dose of investigational product.
9. Most recently determined laboratory values, within 7 days before patient enrollment on this study, satisfy the criteria listed below. If all the laboratory values were obtained over 7 days before the ONO-4538 initial treatment, the laboratory test has to be performed within 7 days before the ONO-4538 initial treatment and the laboratory values have to meet the all criteria listed below.

Laboratory testing must be performed with no granulocyte colony stimulating factor (G-CSF) treatment or blood transfusion having taken place 14 or fewer days before testing.

- WBC count  $\geq 2,000/\text{mm}^3$  and neutrophil count  $\geq 1,500/\text{mm}^3$
- Platelet count  $\geq 100,000/\text{mm}^3$
- Hemoglobin  $\geq 9.0 \text{ g/dL}$
- AST (GOT) and ALT (GPT)  $\leq 3.0$  times the upper limit of normal range of each institute
- Total bilirubin  $\leq 2.0$  times the upper limit of normal range of each institute
- Creatinine  $\leq 1.5 \text{ mg/dL}$  or creatinine clearance (raw or estimated using Cockcroft/Gault formula)  $> 45 \text{ mL/min}$

\* The term “women of childbearing potential” includes all women who have experienced menarche but have not undergone a sterilization procedure (e.g., hysterectomy, bilateral tubal ligation, bilateral oophorectomy) or experienced menopause. Menopause is constituted by having been amenorrheic for at least 12 months without a notable reason. Women who use an oral contraceptive, an intrauterine device, the barrier method, or other mechanical method of contraception are considered to be of childbearing potential.

\* The subject must consent to use any two of the following methods of contraception: vasectomy or condom for patients who are male or their partner and tubal ligation, contraceptive diaphragm, intrauterine device, or oral contraceptive for patients who are female or their partner.

### **3.1.2 Subject Exclusion Criteria**

Patients satisfying any of the following criteria will be excluded:

[figure not shown]
1. Current or prior severe hypersensitivity to another antibody product
2. Adverse drug reactions due to prior treatments or remaining effects of surgical therapy that, in the principal or sub investigator's opinion, may interfere with the evaluation of the investigational product
3. Active autoimmune disease or history of chronic or recurring autoimmune disease (Appendix 3).
4. Current or prior interstitial lung disease or pulmonary fibrosis diagnosed based on diagnostic imaging or clinical findings.
5. Active diverticulitis or symptomatic gastrointestinal ulcerative disease

6. Multiple primary cancers (except for completely resected basal cell cancer, stage I squamous cell carcinoma, carcinoma in situ, intramucosal carcinoma, or superficial bladder cancer or any other cancer from which the patient has been recurrence-free for at least 5 years)
7. Original cancer or metastases to the brain or meninges (unless such lesions are asymptomatic and do not require treatment)
8. Pericardial effusion, pleural effusion, or ascites requiring treatment
9. Cancer pain not stable with a fixed regimen of an analgesic
10. History of transient ischemic attack, cerebrovascular accident, thrombosis, or thromboembolism (pulmonary arterial embolism or deep vein thrombosis) within 180 days of enrollment.
11. Any of the following cardiovascular diseases that are uncontrollable or severe:
  - Myocardial infarction within 180 days of enrollment
  - Uncontrollable angina pectoris within 180 days of enrollment
  - New York Heart Association (NYHA) Grade III or IV congestive cardiac failure
  - Hypertension (systolic blood pressure  $\geq$  150 mmHg or diastolic blood pressure  $\geq$  90 mmHg persisting for  $\geq$  24 hours) despite appropriate treatment
  - Arrhythmia requiring treatment
12. On anticoagulant therapy (other than antiplatelet therapy with low-dose aspirin) or having a disease requiring anticoagulant therapy.
13. A serious concomitant disease such as liver failure, renal failure or uncontrollable diabetes.
14. Patients requiring transplantation or with a history of transplantation except autotransplantation
15. Has received a systemic corticosteroid (unless temporarily for testing, prophylaxis, or a similar purpose unrelated to an autoimmune disease) or an immune suppressant 28 or fewer days before enrollment.
16. Has received an anti-cancer product (e.g., chemotherapy, molecular targeted therapy, and immunotherapy) 28 or fewer days before enrollment.
17. Has undergone surgery for pleural, pericardial, or similar adhesion 28 or fewer days before enrollment.
18. Has undergone surgical treatment accompanying general anesthesia 28 or fewer days before enrollment.
19. Has undergone surgical treatment accompanying local or surface anesthesia 14 or fewer days before enrollment.
20. Has received radiotherapy 28 or fewer days before enrollment or has received radiotherapy for relief of cancer symptoms 14 or fewer days before enrollment.

21. Has received a radiopharmaceutical agent (except when the radiopharmaceutical agent is used for testing or diagnostic purposes) 56 or fewer days before enrollment.
22. Has undergone gamma knife or CyberKnife treatment 14 or fewer days before enrollment.
23. Has a systemic infection that requires treatment.
24. Has tested positive for HIV-1 antibody, HIV-2 antibody, HTLV-1 antibody, HBs antigen, or HCV antibody.
25. Has tested positive for HBs antibody or HBe antibody and has a result of at least detectable in HBV-DNA assay despite testing negative for HBs antigen.
26. Is pregnant, nursing, or possibly pregnant.
27. Has received another investigational product 28 or fewer days before enrollment.
28. Has previously received ONO-4538 (MDX-1106 or BMS-936558), an anti-CTLA-4 antibody, or other antibody therapy or drug therapy intended to control T-cells.
29. Is found incapable of giving consent due to dementia or another such condition.
30. Patients otherwise found by the principal or sub investigator to be ineligible.

#### 4. Study Schedule and Observations

The study consists of a screening phase, treatment phase, and follow-up phase (see [Figure 4](#)).

**Figure 4 Summary of study design**

##### 4.1 Screening Phase

Patients who satisfy all of the subject inclusion criteria and none of the subject exclusion criteria and who are found eligible by the principal or sub investigator can be enrolled and then moved to the treatment phase.

#### **4.2 Treatment Phase**

ONO-4538 will be administered once. Subjects who will meet any of the Criteria for Entering the Follow-Up phase will move to the Follow-Up phase. The subjects who complete the treatment phase in this study and not meet all of the Criteria for Entering the Follow-Up phase, and will satisfy all inclusion criteria and not meet all of the exclusion criteria in the ONO-4538-14 study may move to the ONO-4538-14 study, otherwise the subjects will move to the Follow-Up phase.

#### **4.3 Follow-up Phase**

Those subjects receiving the investigational product who satisfy any of the Criteria for Entering the Follow-Up phase will proceed to the Follow-Up phase.

**Table 4 Study schedule**

1. Begin administering the investigational product within 30 days of informed consent.
2. The data from virus tests performed within 1 year of enrollment, diagnostic imaging (e.g., CT, MRI) performed within 14 days of enrollment will be included.
3. Women of childbearing potential will undergo a serum pregnancy test in the screening phase and subsequently undergo urine pregnancy testing.
4. Other than weight.
5. Also perform at unscheduled visits as necessary if, during the study (from the time of informed consent to the end of the subjects' schedule), signs, subjective and objective symptoms, or test findings suggest respiratory disease.
6. SP-D and KL-6 will be measured in the screening phase and, as necessary, in the treatment phase.
7. Collect blood sample at 24, 48 and 72 hours after the completion of the administration on 2nd, 3rd and 4th day, respectively.
8. [REDACTED]
9. Check for brain metastases with head CT/MRI. Check for bone metastases with X-ray imaging, FDG-PET, or bone scintigraphy as required by the clinical symptoms.
10. Perform tumor marker assessment according to the cancer type of patient when required at Investigator's discretion.

## 5. Dose and Administration, and Duration of Treatment

Patients will be assigned any of the following groups in order of increasing dose and ONO-4538 is administered at a dose level of 1, 3 or 10 mg/kg (See Table 5)

Table 5. ONO-4538 Dose		
Group	Treatment phase	Subjects number
	Dose (mg/kg)	
A	1	6
B	3	6
C	10	6

ONO-4538 will be administered once in the treatment phase and each subject will be observed for 3 weeks. The appropriate dose of ONO-4538 will be diluted with physiological saline to a total amount of approximately not less than 60 mL before use (so that concentration of diluted solution of ONO-4538 is no less than 0.35 mg/mL). The entire dose of ONO-4538 will be administered as an intravenous infusion over approximately 60 minutes through a 0.20 or 0.22 µm in-line filter. The lower limit of the infusion time is 54 minutes. The target upper limit is 90 minutes. At the end of the infusion, the line will be flushed with a sufficient quantity of physiological saline. Regarding the calculation of the dosage amount, the dose can be rounded off to the nearest tenth.

## 6. Prior and Concomitant Therapies

### 6.1 Therapies Prohibited During the Study

The therapies listed below are prohibited during the study (from the time of informed consent to the end of the subjects' schedule).

1. Immunosuppressants and corticosteroids \*1
2. Anti-cancer products (e.g., chemotherapy, molecular targeted therapy, immunotherapy\*2)
3. Surgical treatment for a malignant tumor
4. Radiotherapy
5. Radiopharmaceuticals\*3 and anti-androgen receptor therapy
6. Bisphosphonate products and anti-RANKL antibodies \*4
7. Transplant therapy
8. Any other investigational product

\* Subjects are permitted to use a local corticosteroid such as topical, intra-articular, intranasal, ocular, inhalational administration, or otherwise temporal systemic corticosteroid for the treatment or prevention of a contrast media allergy or an adverse event.

\* This includes local therapies.

\* The use of a radiopharmaceutical for a testing or diagnostic purpose is permitted.

\* Bisphosphonate products and anti-RANKL antibodies may be used only when the dosage regimen used before study enrollment is maintained.

## **7. Criteria for Entering the Follow-Up phase**

Subjects satisfying any of the following criteria in the treatment phase will proceed to the follow-up phase. Only when the subjects do not satisfy all of the following criteria in the treatment phase, the subjects may move to the ONO-4538-14 study.

1. The development of PD is identified by the principal or sub investigator according to the RECIST guideline (version 1.1) only in case in which the unplanned tumor assessment with diagnostic imaging is performed in the treatment phase.
2. It is determined that continuing the treatment is not appropriate because the worsening of clinical symptoms attributed to disease progression occurs.
3. The subject develops Grade 2 or higher interstitial lung disease, regardless of the causal relationship to the investigational product.
4. Grade 2 or greater eye pain, or visual acuity reduced occurs whose causal relationship with the investigational product cannot be ruled out and does not improve to Grade 1 severity with local treatment.
5. Grade 3 or greater bronchospasm, hypersensitivity reaction, infusion reaction (e.g., pyrexia, chills, nausea, pain, headache, cough, pruritus, and rash) or uveitis occurs whose causal relationship with the investigational product cannot be ruled out.
6. The investigator or sub-investigator otherwise determines that continuing to administer the investigational product is inappropriate.

## **8. Endpoints**

### **8.1 Safety**

1. Adverse events

2. Laboratory tests (hematology, blood biochemistry, qualitative urinalysis, immunology, hormone tests)
3. Vital signs (systolic blood pressure/diastolic blood pressure, pulse rate, and body temperature), body weight, percutaneous oxygen saturation (SpO2)
4. 12-lead ECG
5. Chest X-ray
6. Performance Status (ECOG)

## **8.2 Pharmacokinetics**

1. Serum ONO-4538 concentrations
2. Pharmacokinetic parameters such as Cmax, Tmax, AUC, T1/2

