1 INTRODUCTION

ONO-4538 (Bristol-Myers Squibb [BMS] developmental code: BMS-936558, ex-Medarex developmental code: MDX-1106) is a fully human monoclonal antibody to human programmed cell death-1 (PD-1 [also known as CD279]), made by Ono Pharmaceutical Co., Ltd. and Medarex Inc. The product is made with recombinant technology using CHO cells. PD-1 is a receptor of the CD28 family (a molecular group that positively and negatively regulates the activation of T cells in supplementary fashion), which is expressed on activated lymphocytes (T cells, B cells and NKT cells) and myeloid cells. PD-1 binds to PD-1 ligands (PD-L1 [also known as B7-H1 and CD274] and PD-L2 [also known as B7-DC and CD273]), which are expressed on antigen-presenting cells, and transmits regulatory stimuli to lymphocytes to down-modulate the activation of lymphocytes ¹⁾. PD-1 ligands are expressed on various cancer tissues ²⁾, in addition to antigen-presenting cells. Based on some non-clinical pharmacological studies, the proliferation and the activation of antigen-specific T cells have been shown as the result of the inhibition to binding of PD-1 on PD-1 ligand by ONO-4538.

Ono is clinically developing the ONO-4538 in Korea and Japan. BMS is clinically developing that in other regions.

We have planned to conduct a clinical trial to investigate the pharmacokinetics of ONO-4538 in patient with solid tumor in Korea. In addition to the pharmacokinetics, the safety and pharmacological action will be evaluated. The data from this study will be included in the documents for the new drug administration of ONO-4538 in Korea.

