2 STUDY OBJECTIVES

The objective of the study is to investigate the pharmacokinetics of ONO-4538 administered to Korean patients with advanced or recurrent solid tumors who are refractory or intolerant to standard therapy or for whom no appropriate treatment is available.

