3.3.2 Treatment Phase

ONO-4538 will be administered once. Subjects who will meet any of the Criteria for Entering the Follow-Up phase will move to the Follow-Up phase. The subjects who complete the treatment phase in this study and not meet all of the Criteria for Entering the Follow-Up phase, and will satisfy all inclusion criteria and not meet all of the exclusion criteria in the ONO-4538-14 study may move to the ONO-4538-14 study, otherwise the subjects will move to the Follow-Up phase.

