3.3.3 Follow-up Phase

Those subjects receiving the investigational product who satisfy any of the Criteria for Entering the Follow-Up phase will proceed to the Follow-Up phase.

Table 3 Study schedule

Category	Study day	Screening Phase	Treatment Phase									Follow-Up phase	
			1			2	3	4	8	15	22		
			Before administration	After the start of the administration	After the end of the administration	1 hr	2 hr	8 hr					
Allowable range (days)	-7 to -1					-			±2	±3		+3	±7
Written informed consent		○ ¹											
Inclusion/exclusion criteria		○											
Virus tests		○ ²											
ONO-4538 administration			○										
Demographics		○											
Pregnancy test ³		○										○	○
Vital signs/weight		○	○ ⁴	○ ⁴	○ ⁴	○ ⁴	○ ⁴	○ ⁴	○ ⁴	○ ⁴	○ ⁴	○	○
/percutaneous oxygen saturation													
Performance Status		○										○	○
Chest X-ray ⁵		○										○	○
12-lead ECG		○	○	○	○	○	○	○	○	○	○	○	○
Hematology tests/urinalysis		○										○	○
/blood biochemistry tests												○	○
Immunology/hormone tests		○ ⁶										○	○
Serum drug concentration ⁷			○	○	○	○	○	○	○	○	○	○	○
Anti-ONO-4538 antibody			○									○	○
													●
Diagnostic imaging (e.g., CT, MRI) ⁹		○ ²											
Tumor marker ¹⁰							●						
Concomitant drugs/adverse events				←									→

○:essential, ●:optional

1. Begin administering the investigational product within 30 days of informed consent.
2. The data from virus tests performed within 1 year of enrollment, diagnostic imaging (e.g., CT, MRI) performed within 14 days of enrollment will be included.
3. Women of childbearing potential will undergo a serum pregnancy test in the screening phase and subsequently undergo urine pregnancy testing.
4. Other than weight.
5. Also perform at unscheduled visits as necessary if, during the study (from the time of informed consent to the end of the subjects' schedule), signs, subjective and objective symptoms, or test findings suggest respiratory disease.
6. SP-D and KL-6 will be measured in the screening phase and, as necessary, in the treatment phase.
7. Collect blood sample at 24, 48 and 72 hours after the completion of the administration on 2nd, 3rd and 4th day, respectively.
[REDACTED]
9. Check for brain metastases with head CT/MRI. Check for bone metastases with X-ray imaging, FDG-PET, or bone scintigraphy as required by the clinical symptoms.
10. Perform tumor marker assessment according to the cancer type of patient when required at Investigator's discretion.

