3.7 Sample size determination

3.7.1 Planned Number of Subjects

Total 18 subjects (6 subjects in each group)

Rationale

ONO-4538 is a fully human IgG4 monoclonal antibody and it is reported that there is no great distinction between Japanese and non-Japanese regarding the pharmacokinetics of monoclonal antibody. Therefore the sample size which the pharmacokinetics can be evaluated is set at 6 subjects in each group in this study.

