4 ANALYSIS SETS

The “Safety Analysis Set (SAF)” will be used in the safety endpoint evaluation.

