4.1 Definitions of Groups

These sets will be defined as a group of subjects who have provided informed consent. Definitions of the individual groups are shown below.

1) Enrolled Set (ENR)

This set will be defined as group of subjects who have been enrolled.

2) SAF

This set will be defined as group of subjects who included in ENR and have received at least one dose of the study drug.

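### Does the lack of a PK analysis in the SAP, in a study whose only stated objective is PK, call for a change to the plan?

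*Protocol*

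**What the plan says.** SAP section 2 gives one objective: "The objective of the study is to investigate the pharmacokinetics of ONO-4538". The protocol synopsis states the same. Protocol Synopsis 8.2 names serum concentrations and "Pharmacokinetic parameters such as Cmax, Tmax, AUC, T1/2" as endpoints; the AUC interval is not given. SAP 3.7.1 rests the group size on PK: "Therefore the sample size which the pharmacokinetics can be evaluated is set at 6 subjects in each group in this study". SAP section 1 says why the results matter: "The data from this study will be included in the documents for the new drug administration of ONO-4538 in Korea".

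The analysis text covers something else. SAP section 4 says of the Safety Analysis Set that it "will be used in the safety endpoint evaluation", and 4.1 defines it: "This set will be defined as group of subjects who included in ENR and have received at least one dose of the study drug". The only other set is the enrolled set. SAP section 5 documents safety endpoints alone. Sections 6 to 9 cover disposition, exposure, baseline and safety, and section 15 lists no references.

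On sampling, the footnote to SAP Table 3 fixes the early times: "Collect blood sample at 24, 48 and 72 hours after the completion of the administration on 2nd, 3rd and 4th day, respectively". It says nothing about how a follow-up sample is used. On who reaches follow-up, SAP 3.3.2 says that subjects who complete the treatment phase and qualify "may move to the ONO-4538-14 study, otherwise the subjects will move to the Follow-Up phase".

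**The concern.** A SAP normally carries the analysis of the primary objective. Followed literally, this one would give a full safety report and no PK result, although PK is why the study is run and why it has 18 subjects.

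There is a second worry. If serum is drawn at the follow-up visit, subjects who do not join ONO-4538-14 have a longer sampling window than those who do. Joining is closed to subjects with progression or specified toxicity (Protocol Synopsis section 7). An AUC taken to each subject's last sample would then mix exposure with window length, and window length with clinical course. The half-life estimate would also depend on whether the late point enters the slope.

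**Working it through.** **The plan's own figure.** 3 dose groups × 6 = 18, as stated. The documents give no CV, precision target, alpha or power, so no sample-size formula can be checked. SAP 10.2 says that no tests are done.

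**Is PK missing by oversight, or outside this document's scope?**
- The public protocol is a synopsis that ends with the planned study period and has no statistical section.
- SAP section 13 records two changes from the protocol: the enrolled set was added and target-lesion diameter was dropped from the background factors. The synopsis contains neither a list of analysis sets nor a list of background factors, so fuller protocol text exists.
- Section 13 logs the loss of one baseline item but no loss of PK.
- The SAP has no analysis of anti-drug antibody (Protocol Synopsis 8.3) or of the pharmacological action mentioned in its own introduction. PK is not singled out.

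This fits a safety SAP with the other analyses planned elsewhere. It does not prove that a PK plan exists.

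**Size of the AUC effect, if AUC ran to the last sample.** Inputs: Day 22 is 21 days after dosing. A follow-up visit 28 days later is at 49 days, if that is what SAP 4.3 means. Half-life T is not given; 10-25 days is assumed. The fraction of total AUC reached by time t is A(t) = f + (1 − f)(1 − 2^(−t/T)), with f = 0 (mono-exponential) or f = 0.2 (assumed early phase, complete by then).

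| T (days) | A(21), f=0 | A(49), f=0 | Ratio, f=0 | Ratio, f=0.2 |
|---|---|---|---|---|
| 10 | 0.767 | 0.967 | 1.26 | 1.20 |
| 15 | 0.621 | 0.896 | 1.44 | 1.32 |
| 20 | 0.517 | 0.817 | 1.58 | 1.39 |
| 25 | 0.441 | 0.743 | 1.68 | 1.44 |

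If 2 of 6 in a group are completers who do not join (assumption), the group geometric mean is multiplied by ratio^(2/6): 1.26^(1/3) = 1.08 to 1.68^(1/3) = 1.19 for f = 0, and 1.06 to 1.13 for f = 0.2.

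The 49-day figure applies only to completers. A subject who discontinued on Day 8 would have a visit at about 7 + 28 = 35 days, giving ratios of 1.19 to 1.41 (f = 0).

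**Half-life.** With equal log-scale error, the slope's standard error varies as 1/√Sxx. For days 7, 14 and 21, Sxx = 98; adding day 49 gives 1016.75. The ratio is √(98/1016.75) = 0.31, so using a late point, where there is one, is a gain in precision.

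**Does the routine choice work?** Take AUC over 0-21 days for everyone, with actual sampling times. The least favourable case under SAP 4.3 is a Day 22 sample taken 3 days early, at 18 days. The 18-21 day piece is then [A(21) − A(18)]/A(21): 7% at T = 10 and 11% at T = 25 (f = 0). If the half-life used for that piece is wrong by a factor of 2 either way, AUC over 0-21 days is off by at most 0.7%. The joiner/non-joiner difference disappears, and no new sample is needed.

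**Is there a late sample at all?** Ten serum times run from pre-dose to Day 22. The broken Table 3 row can be counted as 11 or 12 marks, so it seems to extend further. Its allowable ranges include both +3 and ±7, and SAP 4.3 lists a discontinuation visit (+3) separately from follow-up (±7). An eleventh mark could belong to either. The follow-up wording in SAP 4.3 and 9.1.2 does not settle the day.

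**The case for a change.** The strongest case for a change is that a SAP should either contain the analysis of the sole objective or say where it is. Sections 13 and 15 were the natural places to say so, and neither does. Pointing to an unseen document does not close the gap, and a cross-reference would cost one sentence. With joining tied to clinical course, leaving the AUC interval and slope points open also allows a choice after the data are seen. The half-life result in particular depends on whether a late sample is used.

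Much of this stands as fact: the silence is there, the AUC interval is unnamed, and the arithmetic is right. What does not follow is that the plan produces a wrong answer. The bias needs AUC to the last sample, which no passage prescribes, plus a late sample, a visit day, half-lives and non-joiner numbers that the documents do not establish. Specifying main parameters, geometric CVs and confidence intervals would be good practice. In a descriptive study without tests, those are largely matters of preference.

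**Conclusion.** The observation is correct but calls for no change. The SAP reads as a safety analysis plan, and the protocol already commits to concentrations, Cmax, Tmax, AUC and half-life. What remains open is detail that a PK analyst settles as routine: dosed subjects with usable concentrations as the set, a common AUC interval with actual times, and stated points for the terminal slope. Cmax and Tmax are unaffected by the length of the window.

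The 26-68% difference between subjects and the 8-19% group shift are illustrations only. They hold for mono-exponential PK, assumed half-lives of 10-25 days, a sample at 49 days and 2 of 6 completers not joining, and they vanish if AUC is taken over 0-21 days. The conclusion rests on reading the SAP as limited in scope. The documents support that reading but do not prove it. If no PK plan existed anywhere, the omission would weigh more, though the samples and endpoints to make it good are already in place.
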